### 8.6.1. Other Clinical Laboratory Tests

At screening, patients will be tested for hepatitis B surface antigen (HBsAg), antibodies to hepatitis C virus (HCV), human immunodeficiency virus (HIV) types 1 or 2, and Tuberculosis test.

COVID-19 testing will be available at the central laboratory. Locally performed COVID-19 testing results will also be accepted.

Human chorionic gonadotropin (HCG) tests in serum and in urine will be performed for women of childbearing potential at the time points detailed in Table 2 (screening and run-in), Table 3 (treatment period), and Table 4 (follow-up) of the study protocol.

At screening, women who have been amenorrheic for at least 1 year without an alternative medical cause will have a serum follicle stimulating hormone (FSH) assessment to confirm postmenopausal status.

Other clinical laboratory tests results will be listed.

### 8.6.2. Laboratory Values Meeting Hy’s Law Criteria

All occurrences of possible drug-induced liver injury that meet Hy’s law criteria as defined in the Section 7.1.5.1 of the study protocol will be included in serious adverse events reporting.

## 8.7. Physical Examinations

Physical examinations will be performed at the time points detailed in Table 2 (screening and run-in), Table 3 (treatment period), and Table 4 (follow-up) of the study protocol. Any physical examination finding that is judged by the investigator as clinically significant (except at the initial screening visit, which will be captured as medical history) may be considered an adverse event, recorded on the CRF, and monitored as described in Section 7.1.2 of the study protocol. Physical exam findings that are attributable to another adverse event or to LoAC/CAEs would not be reported as separate adverse events.

Abnormal physical examination findings will be listed and summarized descriptively.

Height and weight will be obtained at the at the time points detailed in Table 2 (screening and run-in), Table 3 (treatment period), and Table 4 (follow-up) of the study protocol. Data will be summarized and listed with vital signs data.

## 8.8. Vital Signs

Vital signs (blood pressure [systolic/diastolic], respiratory rate, body temperature, and pulse) will be measured at the time points detailed in Table 2 (screening and run-in), Table 3 (treatment period), and Table 4 (follow-up) of the study protocol. Any vital sign value that is judged by the investigator as clinically significant will be recorded both on the source documentation and the CRF as an adverse event, and monitored as described in Section 7.1.2 of the protocol.

Vital signs (including weight) values and changes from baseline to each visit and the Last Assessment will be summarized using descriptive statistics. The incidence of potentially clinically significant abnormal values will be summarized for selected vital signs using descriptive statistics. Baseline is defined as the last observed data before the administration of the first dose of the IMP (also see Section 4.2).

Table 4 specifies the criteria for identifying vital signs as potentially clinically significant abnormal values. Note that in order to qualify as potentially clinically significant abnormal, a value needs to meet both criteria below: ie, have a value beyond the criterion value and a change of at least the magnitude specified in the change relative to baseline column. The potentially clinically significant abnormal vital signs values will include all postbaseline values (including scheduled, unscheduled, and early withdrawal visits) for the summaries.

**Table 4: Criteria for Potentially Clinically Significant Vital Signs**

Vital Sign	Criterion value	Change relative to baseline
Pulse	$\geq 120$ bpm	Increase of $\geq 15$ bpm
	$\leq 50$ bpm	Decrease of $\geq 15$ bpm
Systolic blood pressure	$\geq 180$ mm Hg	Increase of $\geq 20$ mm Hg
	$\leq 90$ mm Hg	Decrease of $\geq 20$ mm Hg
Diastolic blood pressure	$\geq 105$ mm Hg	Increase of $\geq 15$ mm Hg
	$\leq 50$ mm Hg	Decrease of $\geq 15$ mm Hg

**Table 4: Criteria for Potentially Clinically Significant Vital Signs**

Vital Sign	Criterion value	Change relative to baseline
Temperature	≥38.3°C	Change of ≥1.1°C

Bpm=beats per minute

Height will be measured at screening visit, and data will be listed in the vital sign listing.

### 8.9. Electrocardiography

A 12-lead ECG will be recorded at the time points detailed in Table 2 (screening and run-in), Table 3 (treatment period), and Table 4 (follow-up) of the study protocol. ECGs should be performed in a supine position after 5 minutes rest.

All ECG results outside of the reference ranges will be judged by the investigator as belonging to one of the following categories:

- abnormal and not clinically significant
- abnormal and clinically significant

Any ECG finding that is judged by the investigator as clinically significant (except at the screening visit[s]) will be considered an adverse event, recorded on the source documentation and in the CRF, and monitored as described in Section 7.1.2 of the study protocol.

At DoR visit, triplicate measurements are required, each ECG will be taken within 1 to 5 minutes of the previous one. For analysis purpose, the mean of recorded results from the 3 measurements will be calculated and used for the analysis.

Baseline is defined as the last observed data before the administration of the first dose of the IMP. If the last observed data is at DoR visit, the mean of the 3 measurements will be used as the baseline ECG results and the worst value of the 3 recorded findings will be used as the baseline ECG finding.

ECG variable results and changes from baseline to each visit and the Last Assessment will be summarized using descriptive statistics.

Baseline ECG findings and shifts (normal, abnormal not clinically significant, and abnormal clinically significant) from baseline to each visit, overall (worst value for a patient), and the Last Assessment will be summarized using patient counts.

### 8.10. Concomitant Medications or Therapies

Concomitant medications, treatments, or procedures will be collected up to the end of study.

All concomitant medications will be coded using the WHO Drug. The incidence of concomitant medications will be summarized using descriptive statistics by therapeutic class and preferred term. Patients are counted only once in each therapeutic class category, and only once in each preferred term category. The concomitant medications will include all medications taken after administration of the first IMP.

Asthma medications will be summarized by the medication class separately.

## **9. TOLERABILITY VARIABLES AND ANALYSIS**

Number (%) of patients who did not complete the study due to adverse events will be summarized descriptively.

## **10. PHARMACOKINETICS/PHARMACODYNAMICS (PK/PD) ANALYSIS**

Pharmacokinetic serum concentration results for TEV-48574 will be tabulated descriptively and listed at each planned sampling time point using pharmacokinetic analysis set.

PK/PD analyses are outside of the scope of this SAP.

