If a patient contracted and recovered from COVID-19 more than 6 weeks prior to screening, and the patient was not admitted to a hospital's ICU during that COVID-19 infection, and if the patient's symptoms from COVID-19 completely resolved back to pre-COVID-19 status (no lingering anosmia, weakness, persistent dyslogia or feelings of dysphoria for many months after the infection resolved), then the patient may enroll in the trial. The principal investigator should determine whether or not the subject has truly recovered back to his/her usual pre-COVID -19 status and is eligible for enrollment in the study.

[figure not shown]
An e-diary will be dispensed at the second screening visit (Visit S2), 2 weeks (± 3 days) after the initial S1 screening visit. Patients who meet all inclusion criteria (except for eosinophil counts if assessment is incomplete) and none of the exclusion criteria are eligible to enter the run-in and have their ICS+LABA standardized with study-provided ICS+LABA (background asthma controller therapy) at Visit S2; this should start at least 2 weeks prior to randomization and marks the start of run-in. At the end of run-in, patients who continue to meet all of the inclusion criteria, none of the exclusion criteria, and all of the randomization criteria will be eligible to be randomized to TEV-48574 ([REDACTED]).

[REDACTED]. For patients who are randomized, the standardized

ICS+LABA dose must be maintained and the patient held stable on that dose for the first 4 weeks of the treatment period, followed by a structured decrease in background asthma controller therapies for patients not meeting criteria for LoAC. Patients will be monitored via hand-held spirometry and e-diary daily, including between visits, throughout the study. Patients who experience an event of LoAC will be treated by the investigator, discontinue IMP, restart (or increase) background asthma controller therapies, and remain in the study and complete all remaining visits, procedures and assessments, except for IMP administration. The total duration of patient participation in the study is planned to be up to approximately 30 weeks.

The screening and run-in, treatment, and follow-up periods are described below; the study schematic diagram is presented in Figure 1.

Figure 1: Overall Study Schematic Diagram

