7.3. Pregnancy

Any female patient becoming pregnant during the screening period will be considered a screen failure and will not be allowed to rescreen.

Any female patient becoming pregnant during the study will discontinue IMP.

All pregnancies of women participating in the study and female partners of men participating in the study, if applicable, that occur during the study, or within 5 half-lives (~10 weeks) of the last IMP administration, are to be reported immediately to the individual identified in the Clinical Study Personnel Contact Information section of this protocol, and the investigator must provide the sponsor (LSO/CRO) with the completed pregnancy form. The process for reporting a pregnancy is the same as that for reporting a serious adverse event but using the pregnancy form (Section 7.1.5.3).

All female patients and female partners of men participating in the study (female partners of men participating in the study who become pregnant will be asked to sign an ICF) who become pregnant will be monitored for the outcome of the pregnancy (including spontaneous, elective, or voluntary abortion). If the pregnancy continues to term, the outcome (health of the infant up to 8 weeks of age), including details of birth and presence or absence of any birth defect, congenital abnormalities, or maternal and newborn complications, will be reported to the sponsor. Any complication of pregnancy during the study and any complication of pregnancy that the investigator becomes aware of after withdrawal from the study will be reported as an adverse event or serious adverse event, as appropriate.

If the pregnancy in the woman participating in the study and/or the female partners of men participating in the study does not continue to term, 1 of the following actions will be taken:

- For a spontaneous abortion, report as a serious adverse event.
- For an elective abortion due to developmental anomalies, report as a serious adverse event.
- For an elective abortion **not** due to developmental anomalies, report on the pregnancy form; do not report as an adverse event.

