9.9.1. Population Pharmacokinetics

All patients in the safety analysis set who have at least 1 measurable concentration of TEV-48574 will be included in the analysis of pharmacokinetic data. Serum concentrations will be expressed in mass per volume units. All concentrations below the limit of quantification or missing data will be labeled as such in the concentration data listings. TEV-48574 concentration data will be summarized by visit and treatment group. In addition to mean, standard deviation, coefficient of variation, median and quartiles, the geometric mean and geometric coefficient of variation and n(log) will be presented. Pharmacokinetic data per TEV-48574 study treatment may be analyzed with a population-pharmacokinetic mixed effects model. The analysis will be based on a pooled data set, including pharmacokinetic data from previous studies and will be reported in the PAR.

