#### 1.5. Pharmacokinetic Assessment

Pharmacokinetic endpoints are

- Trough serum TEV-48574 concentrations throughout the study (sparse sampling)
- Population pharmacokinetic analysis of pharmacokinetic data

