### **3.5. Pharmacokinetic Analysis Set**

The pharmacokinetic analysis set will include those patients in the safety analysis set who have at least 1 measurable concentration of TEV-48574.

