### **4.4. Study Days and Visits**

For by-visit summaries, if there are multiple assessments at a postbaseline visit then the last non-missing assessment at that visit will be used for the summary (this includes scheduled and unscheduled assessments), except for triplicate ECG assessments (see Section 8.9 for further details).

Study visits are in [Table 1](#). See the study protocol Table 2 to 4 for details.

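### The by-visit trough summaries pool on-dose troughs with samples taken after IMP was stopped, so late-visit exposure is understated

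*SAP*

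**What the plan says.** SAP 1.5 gives the concentration endpoint as "Trough serum TEV-48574 concentrations throughout the study (sparse sampling"). SAP 3.5 defines the analysis set as "those patients in the safety analysis set who have at least 1 measurable concentration of TEV-48574". This is a condition on the patient, not on the sample. SAP 10 then plans the output: "Pharmacokinetic serum concentration results for TEV-48574 will be tabulated descriptively and listed at each planned sampling time point using pharmacokinetic analysis set". Protocol 9.9.1 is similar: "TEV-48574 concentration data will be summarized by visit and treatment group". SAP 4.1 and Protocol 9.9.1 between them plan the mean, median and geometric mean.

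On what happens after LoAC, Protocol 3.1 has patients stop IMP, "remain in the study and complete all remaining visits, procedures and assessments, except for IMP administration". Protocol 4.4.2 encourages patients who stop IMP for other reasons to keep their visits too. Protocol Tables 3 and 4 schedule serum drug concentration at weeks 0, 2, 4, 8, 12, 16 and 24. A patient who stops after the week 6 dose is therefore still due a sample at weeks 8, 12, 16 and 24.

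**The concern.** A trough is the concentration at the end of a dosing interval. A week-16 sample from a patient last dosed at week 6 is a washout value, yet it would enter the week-16 trough row. In a proof-of-concept trial that row is where a reader looks to see whether the intended exposure was reached. The distortion grows with the number of patients who lose control, so it is worst if the drug does not work. That is also when the question of adequate exposure matters most.

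Three existing rules might have removed these samples, and none does:

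- The rule discarding observations after the patient's treatment period (last dose plus 14 days, SAP 1.7) is written only for efficacy endpoints (SAP 6.3.2 to 6.3.4 and 6.4.3 to 6.4.6).
- The SAP 4.4 rule on early-withdrawal visits covers only patients who leave the study.
- The exclusion in Protocol 9.2.4 is discretionary and limited to important deviations. Protocol 4.4.1 treats stopping for LoAC as planned conduct.

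**Working it through.** The plan gives no figure for this bias, so there is none to reproduce.

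**Inputs from the documents**
- Half-life: Protocol 7.3 has "within 5 half-lives (~10 weeks) of the last IMP administration", so 10 / 5 = 2 weeks.
- Dosing every 2 weeks, last dose at week 14 (Protocol 3.1).
- LoAC rate p: 10.8% (design effect) or 27% (no effect), from SAP 2.4.
- 62 randomised patients per arm (SAP 2.4).

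**Assumptions**
- Mono-exponential decline from a steady-state trough.
- LoAC uniform over weeks 4 to 16.
- Every LoAC patient attends every later draw.
- Other IMP stoppers are ignored.

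**Formulas.** With w weeks since the last dose, a sample relative to a true trough is r = 0.5^((w − 2)/2). The pooled arithmetic mean relative to the on-dose mean is 1 − p(1 − mean r). The geometric ratio is 2^(−p × mean number of extra half-lives).

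**Week 16.** LoAC falls in each of six 2-week intervals with probability 1/6. The last dose is at week 4, 6, 8, 10, 12 or 14, so w = 12, 10, 8, 6, 4, 2 and r = 0.03125, 0.0625, 0.125, 0.25, 0.5, 1.
- Mean r = 1.96875/6 = 0.328. Mean extra half-lives = (5+4+3+2+1+0)/6 = 2.5.
- At 10.8%: arithmetic 1 − 0.108 × 0.672 = 0.927; geometric 2^(−0.27) = 0.829.
- At 27%: arithmetic 1 − 0.27 × 0.672 = 0.819; geometric 2^(−0.675) = 0.626.
- Off-dose share is 5/6 of p: 9.0% (about 6 of 62) or 22.5% (about 14 of 62). LoAC after the week 14 dose still leaves a valid week-16 trough.

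The same steps give the earlier visits:

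| Visit | Off-dose share, 10.8% / 27% | Arithmetic ratio | Geometric ratio |
|---|---|---|---|
| Week 8 | 1.8% / 4.5% | 0.991 / 0.977 | 0.988 / 0.969 |
| Week 12 | 5.4% / 13.5% | 0.962 / 0.904 | 0.928 / 0.829 |
| Week 16 | 9.0% / 22.5% | 0.927 / 0.819 | 0.829 / 0.626 |

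**Sensitivity at week 16**
- LoAC uniform over weeks 0–16: ratios 0.919 and 0.769 at 10.8%; 0.797 and 0.519 at 27%.
- LoAC concentrated in weeks 6–10: 0.902 and 0.770; 0.755 and 0.519.
- Half-life 1.5 to 3 weeks (LoAC over weeks 4–16 or 6–10): arithmetic mean 6–10% low at 10.8% and 16–26% low at 27%; geometric mean 12–30% and 27–58% low.

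**Week 24.** The end-of-study sample is 10 weeks after the last planned dose even in completers: 0.5^((10 − 2)/2) = 0.0625 of trough.

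**A workable cut-off.** Visits are fixed to study day, each with ±3 days (Protocol Table 3). A week 14 dose on day 96 and an end-of-treatment sample on day 116 are both compliant and 20 days apart. After one missed dose the shortest compliant gap is 28 − 6 = 22 days. A 20-day limit therefore separates the two groups, whereas 14 + 3 = 17 days would discard compliant troughs.

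**The case against.** The strongest reply is that nothing is lost. Dose and sample times are recorded (Protocol 8.1), and concentrations and IMP administration are both listed (SAP 10 and 8.2). Population PK is the other named endpoint, and a model that uses dose times can account for stopped dosing. Protocol 9.9 also defers detail to a Modeling Analysis Plan that is not available here. This limits the harm, but it does not correct the table planned in SAP 10.

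A reader might go further and infer that the tables will show low exposure falsely linked to loss of control. The documents do not support that. No planned summary is by LoAC status, PK/PD is outside the SAP, and Protocol 9.9.2 leaves modelling optional. The extra sample sought at the time of LoAC (Protocol 6.1.1) would lie close to the last dose and works against such an impression. The risk is confined to ad hoc reading or exploratory graphics.

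A reader might likewise infer that the comparison of ADA status with PK is contaminated. It is only something that may be assessed (Protocol 9.10), immunogenicity analysis is outside the SAP (SAP 12), and no method is stated.

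Finally, SAP 4.4 says that "the last non-missing assessment at that visit will be used for the summary (this includes scheduled and unscheduled assessments"). This could let an event-triggered post-dose sample displace the scheduled one. However, SAP 10 refers to planned time points, which can be read as overriding the general rule. This is an ambiguity to close, not an established error.

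**Conclusion.** The concern holds for the descriptive PK tables. As written, the by-visit summaries of a trough endpoint include off-dose samples, no rule prevents it, and the direction is downward. The bias is negligible at week 8 under the base assumptions and largest at week 16. There it is about 7% (arithmetic) and 17% (geometric) at the design LoAC rate, or about 18% and 37% if the drug has no effect. The median moves less, since at most 27% of patients are off dose through LoAC.

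The size rests on assumed LoAC timing and on a half-life taken from a rounded reporting window; the direction does not. The documents do not say how many patients will stop IMP for other reasons and stay. Such patients would add off-dose samples, while LoAC patients who miss later draws would reduce them. The primary test is not touched. The change is worth making because it is cheap and the affected endpoint is a declared one.

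**What to change.** In SAP 10, derive time since last IMP dose for every concentration sample, then:

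- Summarise by visit only scheduled pre-dose (or end-of-treatment) samples taken within one dosing interval plus both visit windows of the last dose, that is, up to 20 days.
- Tabulate samples taken after IMP discontinuation or a missed dose separately, by time since last dose.
- Label the week 24 sample as washout.
- State that the PK table uses the scheduled pre-dose sample and that event-triggered samples are listed separately, so that the SAP 4.4 rule does not apply.
- Keep all samples in the population PK dataset.

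The cost is a few sentences and one derived flag from dates already collected. Late-visit trough rows lose some patients: at week 16, under the base assumptions, about 6 of 62 at 10.8% LoAC or 14 of 62 at 27%.

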## **11. BIOMARKER ANALYSIS**

Biomarker analysis is outside of the scope of this SAP.

Listing of patients' biomarker data may be provided if applicable.

## **12. IMMUNOGENICITY ANALYSIS**

Immunogenicity analyses are outside of the scope of this SAP.

Listing(s) of patients with positive ADA sample(s) and patient ADA status will be provided if applicable.

### 13. PLANNED INTERIM ANALYSIS

An unblinded interim analysis is planned after the first 40-52 randomized patients have completed the treatment period, experienced LoAC, or withdrawn from the study completely. The main purposes of the interim analysis include a sample size re-assessment and a futility analysis, which will be described in sections 13.1 and 13.2 below.

The interim analysis will be conducted by an independent, unblinded statistician who is not a part of the study team. A group of the sponsor’s management team who are not a part of the study team may have access to the unblinded interim analysis results. A communication plan to ensure the maintenance of the study blind among the blinded personnel involved in the conduct of the study will be specified in an interim analysis charter prior to the interim analysis.

#### 13.1. Sample Size Re-Assessment

The assumed LoAC event rate in the placebo group is 0.270. If the actual placebo event rate is lower than expected, the study will be underpowered to detect a 60% reduction in event rate. At the interim analysis, if the observed placebo event rate is lower than expected, and the observed treatment effect is at least a 40% reduction (event rate ratio  $\leq 0.6$ ), the sample size may be increased by up to 50 additional randomized patients, from the initially planned 124 to up to 174. This procedure corresponds to a Promising Zone methodology and does not increase the Type I error rate (Mehta and Pocock 2011). Using an exhaustive enumeration of all possible trial outcomes, it is verified that the type I error rate is preserved when the interim unblinded sample size re-assessment is implemented:

**Table 5: Calculated Type 1 Error Rates with or without Sample Size Re-assessment**

True Placebo Event Rate	Fixed Sample Size Design	Adaptive Sample Size Design
0.12	10.5%	9.5%
0.15	10.3%	9.7%
0.18	10.3%	10.0%
0.21	10.4%	10.2%
0.24	10.2%	10.1%
0.27	10.1%	10.0%
0.30	10.3%	10.3%
0.33	10.6%	10.6%
0.36	10.7%	10.7%
0.39	10.3%	10.3%
0.42	9.7%	9.7%
0.45	9.2%	9.2%

